5. VARIABLES

5.1. EFFICACY VARIABLES

PRIMARY VARIABLE

The primary variable of the study is the change from baseline to Week 8 in LDL cholesterol levels.

SECONDARY VARIABLES

The secondary variables of the study are defined as change from baseline to Week 8 in:

- Total blood cholesterol
- Blood HDL-cholesterol
- Blood non-HDL cholesterol
- Blood triglycerides
- Apolipoprotein B
- TC/HDL and LDL-C/HDL risk ratios
- Pulse Volume (PV) waveform (endothelial reactivity)
- Glycemia, ALT, AST, gamma-GT, creatinine, uric acid, CPK

5.2. SAFETY VARIABLES

Other variables are as follows:

- Change from baseline at each assessment time point for each laboratory parameter
- Adverse Events
- Vital Signs
- Weight
- Height
- Waist Circumference
- Index of Central Obesity (ICO)
- Body Mass Index (BMI)
- Hepatic Steatosis Index (HSI)
- Lipid Accumulation Product (LAP)

Statistical Analysis Plan

Sponsor: A. Menarini Industrie Farmaceutiche Riunite S.r.l.

Protocol number: MEIF/16/MOF-Col/001

6. DEFINITION AND GENERAL METHODOLOGY

6.1. GENERAL METHODOLOGY

Statistical tables, figures, listings and analyses will be produced using SAS® for Windows release 9.4 (64-bit) or later (SAS Institute Inc., Cary, NC, USA). Continuous data will be summarized by mean, standard deviation (SD), median, 1st and 3rd quartile, minimum and maximum. Categorical data will be presented by absolute and relative frequencies (n and %) or contingency tables. Percentages will be computed considering subjects with non-missing information, if not differently specified.

DEFINITION OF BASELINE

The baseline period for the present study is defined as the visit 2 (Day 0 – baseline).

CODING OF THERAPIES AND MEDICAL TERMS

Baseline medical history, pre-existing conditions and adverse events will be coded using the Medical Dictionary for Regulatory Activities (MedDRA dictionary, English version 20.0). Prior and concomitant medications will be coded using the WHO Drug Dictionary version B2 Q4 2016.

MISSING OR PARTIAL DATES

For the computation involving dates, the following assumption will be made in case of partially missing information:

- Day missing => day will be replaced with 15
- Day and month missing => day will be replaced with 1, month will be replaced with 7
- Day, month and year missing => no imputation will be done

HANDLING OF MISSING DATA/IMPUTATION RULES/CENSORING RULES

No missing data imputation will be adopted.

HANDLING OF DROP-OUT PATIENTS

Not applicable.

MULTIPLICITY ISSUES

No alpha level adjustment for multiplicity will be adopted.

6.2. STUDY PATIENTS

The number and percentages of screened subjects and reason for screening failure will be summarized overall.

Statistical Analysis Plan

Sponsor: A. Menarini Industrie Farmaceutiche Riunite S.r.l.

Protocol number: MEIF/16/MOF-Col/001

A complete description of patients' disposition will be provided, overall and by planned treatment group specifying the number of randomized patients, the number of patients at each visit, the number of completed and discontinued patients and the reason for the discontinuation.

The number of protocol and non-protocol deviations and the number of patients per deviation will be summarized.

The numerosness of the analysis populations will be described and the reason excluding the subject from any analysis population will be provided.

PATIENTS DEMOGRAPHICS AND OTHER BASELINE CHARACTERISTICS

Patient demographics and baseline characteristics will be summarized on the FAS Population, overall and by planned treatment group, by means of summary descriptive statistics.

Demographic characteristics for patients will include sex, race and age at screening (years). Patients' age at screening will be calculated as the number of completed years since birth at the time of informed consent.

Medical history will be presented by MedDRA System Organ Class (SOC) and Preferred Term (PT). Ongoing status at informed consent will be also taken into account.

Background characteristics will include the following variables:

- Anthropometric data performed at baseline include weight (Kg), height (m), Body Mass Index (BMI), waist circumference (cm), Index of Central Obesity (ICO), Hepatic steatosis Index (HSI), Lipid Accumulation Product (LAP).
- Vital signs at baseline include heart rate, systolic blood pressure (SBP) and diastolic blood pressure (DBP) calculated as average of three measurements both in orthostatic position and clinostatic position. The three measurements collected in orthostatic position and clinostatic position will be only listed.
- Pregnancy test for women not childbearing potential was assessed at baseline. Result of urine pregnancy test (positive/negative) will be described.
- Endothelial reactivity was performed at baseline and results include baseline brachial pulse volume (PV1), brachial pulse volume after hyperemia (PV2) and pulse volume (PV) waveform (endothelial reactivity) calculated as the root-square of ratio PV2/PV1 will be described.
- Diet Evaluation include data about style diet followed by patients at screening (i.e. Mediterranean-style diet Yes or No), information about diet suggestion to correct

Statistical Analysis Plan

Sponsor: A. Menarini Industrie Farmaceutiche Riunite S.r.l.

Protocol number: MEIF/16/MOF-Col/001

unhealthy habits received or not by patients at screening visit and patient compliant with the diet suggestion at baseline.

- Hematology parameters include total cholesterol, LDL-cholesterol, HDL and non-HDL cholesterol, triglycerides, TC/HDL and LDL-C/HDL risk ratio, B apolipoproteins, LDL-C/Apo B.
- Chemistry parameters include glycemia, ALT, AST, gamma-GT, CPK, uric acid, creatinine, eGFR with MDRD formula.

6.3. PRIOR AND CONCOMITANT MEDICATIONS

Prior and concomitant medications are collected during the study together with their indication, dosage, unit, route of administration and frequency.

Prior medications are defined as therapies starting prior to the study and ending prior to the start of study treatment (i.e. date of first intake).

Prior medications will be presented by ATC Code Level 2, Preferred Term and ongoing status overall and by planned treatment group on the FAS Population.

Concomitant medications are defined as therapies ending or ongoing after the start of study treatment. Concomitant medications will be presented by ATC Code Level 2, Preferred Term and ongoing status overall and by actual treatment group on the Tolerability population.

A medication with a missing start date will be assumed to be a concomitant medication, unless the stop date is before the first dosing date in which case the medication will be summarized as a prior medication. Medications with start dates before the dosing date and missing end dates or end dates after the first dosing date will be summarized as concomitant medications.

6.4. DRUG EXPOSURE AND TREATMENT COMPLIANCE

Extent of exposure to study treatment is defined as the difference in days between the date of last administration and the date of first treatments administration plus one, regardless of unplanned intermittent discontinuation.

Overall treatment compliance is defined as the actual number of tablets taken compared to the treatment duration (i.e. extent of exposure). Compliance levels are defined as following according to overall treatment compliance:

- < 80%
- <80% and ≤120%
- >120%

A patient that has taken at least 80% and no more than 120% of the required treatment will be considered compliant.

Statistical Analysis Plan

Sponsor: A. Menarini Industrie Farmaceutiche Riunite S.r.l.

Protocol number: MEIF/16/MOF-Col/001

The number and percentage of patients with at least one dose reduction or interruption will be described. The reason for dose reduction or interruption will be only listed.

Extent of exposure and compliance will be summarized by means of descriptive statistics, overall and by actual treatment group on Tolerability population.

6.5. EFFICACY EVALUATION

6.5.1. Primary efficacy analysis

The statistical analysis of the primary variable will be performed on the FAS population. Summary statistics of LDL cholesterol levels and change from baseline at each assessment time point will be presented overall and by planned treatment group by means of descriptive statistics for continuous data.

An analysis of covariance (ANCOVA) model will be estimated on the changes from baseline to Week 8 in LDL cholesterol levels considering planned treatment group as factor and baseline value of LDL cholesterol as continuous covariate. Results will be reported as Least-Square Means together with associated two-tailed 95% CI; the difference between Least Square Mean of nutraceutical combination group versus placebo will be estimated with two-tailed 95% CI and p-value.

If the assumption of normality of residuals is violated, the ANCOVA model will be fitted on rank transformed data.

6.5.2. Sensitivity analysis on primary endpoint

The same statistical analysis of the primary variable will be performed on the PP population as supportive.

6.5.3. Secondary efficacy analysis

The statistical analyses of the secondary variables will be performed on the FAS population. Summary statistics for each secondary variable (i.e. total blood cholesterol, blood HDL-cholesterol, blood non-HDL cholesterol, blood triglycerides, apolipoprotein B, TC/HDL and LDL-c/HDL risk ratios, pulse volume(PV) waveform, glycemia, ALT AST, gamma-GT, creatinine, uric acid, CPK) and change from baseline at each assessment time point will be presents overall and overall and by planned treatment group by means of descriptive statistics for continuous data.

For each secondary variable, an analysis of covariance (ANCOVA) model will be estimated on the changes from baseline to Week 8 considering planned treatment group as factor and baseline value of the parameter as continuous covariate. Results will be reported as Least-Square Means together with associated two-tailed 95% CI; the difference between Least

Square Mean of nutraceutical combination group versus placebo will be estimated with two-tailed 95% CI and p-value.

If the assumption of normality of residuals is violated, the ANCOVA model will be fitted on rank transformed data.

6.5.4. Exploratory efficacy analysis

The following exploratory efficacy analysis will be performed on the FAS population:

- Summary statistics of LDL cholesterol levels and change from baseline at each assessment time point will be presented focusing on patient subgroups of clinical interest.
 - Patients with baseline levels of LDL cholesterol
 - Ranging from 115 mg/dl to 159 mg/dl
 - Equal or greater than 160 mg/dl
 - Patients with baseline values of eGFR (computed according to the MDRD formula)
 - Ranging from 60 and 89 ml/min/1.732m²
 - Equal or greater than 90 ml/min/1.732m²
 - Patients with/without Metabolic Syndrome
According to the 2009 Joint Interim Statement, the Metabolic Syndrome is defined as the presence of an abdominal circumference >102 cm for men or >88 cm for women, and two or more of the following criteria:
 - Glucose in fasting conditions ≥ 100 mg;
 - SBP ≥ 135 mmHg or DBP ≥ 85 mmHg or current treatment with antihypertensive drugs;
 - Triglycerides >150 mg/dl;
 - HDL <40 mg/dl for men, <50 mg/dl for women
 - Patients with/without glucose in fasting conditions altered, defined as glucose in fasting conditions out of the following range: from 100 mg/dl and 125 mg/dl.
 - Patients with/without proved hypertension, i.e. patients with SBP ≥ 140 mmHg and/or DBP ≥ 90 mmHg for three consecutive readings performed in orthostatic position.
- Linear regression analysis on LDL change at Week 8 vs. baseline will be performed considering patients age, gender and BMI as predictors.
In case of violation of the assumption of normality of residuals, the linear regression model will be fitted on appropriate transformed data (i.e. rank transformed data, logarithmic transformed data).
- Linear regression analysis on LDL change at Week 8 vs. baseline will be performed considering patients eGFR and glycemia values at baseline as predictors.

Statistical Analysis Plan

Sponsor: A. Menarini Industrie Farmaceutiche Riunite S.r.l.

Protocol number: MEIF/16/MOF-Col/001

In case of violation of the assumption of normality of residuals, the linear regression model will be fitted on appropriate transformed data (i.e. rank transformed data, logarithmic transformed data).

- Linear regression analysis on endothelial reactivity change at Week 8 vs. baseline will be performed considering patients age, gender and BMI as predictors. In case of violation of the assumption of normality of residuals, the linear regression model will be fitted on appropriate transformed data (i.e. rank transformed data, logarithmic transformed data).
- Linear regression analysis on endothelial reactivity change at Week 8 vs. baseline will be performed considering patients eGFR and glicemia values at baseline as predictors.

In case of violation of the assumption of normality of residuals, the linear regression model will be fitted on appropriate transformed data (i.e. rank transformed data, logarithmic transformed data).

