## Menarini Group

Sponsor: A. Menarini Industrie Farmaceutiche Riunite S.r.l.

Amended Protocol Version 4.0 of 16.04.2018

Study Code: *MEIF/16/MOF-Col/001*

- Uncontrolled diabetes mellitus based on PI judgment
- Chronic renal failure (defined as  $eGFR < 60 \text{ ml/min/1.73m}^2$ ) or liver failure (defined as AST and /or ALT  $> 3$  Upper Limit of Normal) (ULN)
- Body Mass Index  $> 32 \text{ kg/m}^2$
- Therapy with statins or other drugs or supplements with effects on lipid metabolism
- Patients with acquired immunodeficiency
- Treatment with immunosuppressants
- Pregnant or breastfeeding women
- Women of childbearing potential not willing to use effective birth control methods
- Patients participating in or having participated in another clinical trial within the previous 3 months
- Current or recent history of drug or alcohol addiction based on PI judgment

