## Menarini Group

Sponsor: A. Menarini Industrie Farmaceutiche Riunite S.r.l.

Amended Protocol Version 4.0 of 16.04.2018

Study Code: MEIF/16/MOF-Col/001

- BMI = Weight (kg) / Height (m)
- ICO = Ratio of Waist Circumference and Height (cm) (13)
- HSI = 8 x (ALT/AST ratio)+BMI (+2, if female; +2, if diabetes mellitus) (14)
- LAP for men = (waist circumference [cm] – 65) × (triglyceride concentration [mmol/l]) (15)
- LAP for women = (waist circumference [cm] – 58) × (triglyceride concentration [mmol/l]) (15)

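### The Metabolic Syndrome rule in SAP 6.5.4 credits drug-treated blood pressure but not drug-treated glucose, so a treated diabetic with fasting glucose below 100 mg/dL can be filed as without the syndrome

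*SAP*

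**What the plan says.** SAP 6.5.4 (Exploratory efficacy analysis) plans summary statistics of LDL cholesterol, and of its change from baseline, for patients with and without Metabolic Syndrome. SAP 2.3 names the syndrome among the baseline characteristics used to classify patients.

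The rule requires "the presence of an abdominal circumference >102 cm for men or >88 cm for women, and two or more of the following criteria". The four items are:

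- Glucose: "Glucose in fasting conditions ≥ 100 mg". The unit is given as mg; mg/dL is evidently meant, as in the altered-glucose subgroup of the same section.
- Blood pressure: "SBP ≥ 135 mmHg or DBP ≥ 85 mmHg or current treatment with antihypertensive drugs".
- Triglycerides: "Triglycerides >150 mg/dl".
- HDL: "HDL <40 mg/dl for men, <50 mg/dl for women".

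On who may enrol, Protocol 7.2 and SAP 3.3 exclude "Uncontrolled diabetes mellitus based on PI judgment", with no glucose cut-off and no ban on glucose-lowering drugs by name. The Hepatic Steatosis Index formula in Protocol 9.3 carries a diabetes term ("2, if diabetes mellitus"). Drugs and supplements acting on lipid metabolism are excluded at entry and prohibited during the study (Protocol 7.2 and 8.6; SAP 3.3 and 3.5).

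**The concern.** Two treatable conditions are scored by different logic within one definition, and the SAP gives no reason. A hypertensive patient whose drug has normalised the reading keeps the blood-pressure item. A diabetic patient whose drug has normalised fasting glucose loses the glucose item. The triglyceride and HDL items have no treatment clause either, but the exclusion of lipid-acting drugs makes one largely unnecessary there. Glucose is therefore the one item that a permitted treatment can mask with nothing in the rule to catch it.

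What is at stake is the make-up of one pair of exploratory subgroups. Any misfiling goes one way, from with to without. In a full analysis set of roughly 70 patients, one or two moved patients could shift a subgroup mean.

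**Working it through.** The plan states no figure on this point, so there is none to reproduce. The check is on the rule itself.

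**Step 1. Write the rule down.** Let W be the waist criterion, and G, B, T and H the glucose, blood-pressure, triglyceride and HDL items, each 0 or 1.

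- As written: syndrome present if W = 1 and G + B + T + H ≥ 2, where G = 1 only if measured fasting glucose is 100 or more.
- With a treatment clause: the same, but G is replaced by G′, where G′ = 1 if glucose is 100 or more or the patient is on glucose-lowering treatment. For a treated patient G′ is always 1.

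**Step 2. Enumerate.** Five binary items give 2⁵ = 32 patterns. For a patient on glucose-lowering treatment:

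| Pattern | Number | As written | With clause | Changes? |
|---|---|---|---|---|
| W = 0 | 16 | without | without | no |
| W = 1, G = 1 (glucose ≥ 100) | 8 | the same under both rules | the same under both rules | no |
| W = 1, G = 0, B + T + H = 0 | 1 | without | without | no |
| W = 1, G = 0, B + T + H = 1 | 3 | without | with | **yes** |
| W = 1, G = 0, B + T + H ≥ 2 | 4 | with | with | no |

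The total is 16 + 8 + 1 + 3 + 4 = 32. Three patterns change, all from without to with. These are counts of logical patterns, not probabilities: the patterns are not equally likely.

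**Step 3. A worked case (illustrative values).** A man has a waist of 104 cm, takes an antihypertensive and an antidiabetic, and has fasting glucose 95, triglycerides 120 and HDL 45 mg/dL. Then W = 1 (104 > 102), G = 0 (95 < 100), B = 1 (treated), T = 0 (120 is not above 150) and H = 0 (45 is not below 40). As written the score is 0 + 1 + 0 + 0 = 1, so he is without the syndrome. With the clause it is 1 + 1 + 0 + 0 = 2, so he is with it.

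**Step 4. How many patients.** The documents give no prevalence of treated diabetes, so what follows is assumption.

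- Analysed patients: 90 randomised (Protocol 7) × (1 − 0.20 dropout, Protocol 11.2) = 72.
- Assume 5% to 15% are treated diabetics and one third of those have fasting glucose below 100.
- Patients losing the glucose item: 72 × 0.05 / 3 = 1.2 to 72 × 0.15 / 3 = 3.6, or about 1 to 4.

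That counts lost items. Patients actually misfiled are the subset with W = 1 and exactly one of B, T and H positive, so 1 to 4 is an upper bound under these assumptions. If, as a further assumption, 20% to 60% of them fall in that subset, the count is 1.2 × 0.2 = 0.24 to 3.6 × 0.6 = 2.16, or about 0 to 2 patients across both arms.

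**The case against.** The strongest reply is that this is an operational choice, not a contradiction. SAP 6.5.4 uses measured-only rules elsewhere: the altered-glucose and proved-hypertension subgroups ignore treatment too. The section also attributes the definition to an outside consensus statement that cannot be consulted here, so nothing can be said about whether the glucose item departs from it. That is right, and the point does not rest on the source. It rests on the asymmetry inside this one definition, which credits treatment for one condition and not for the other.

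It can also be said that few such patients will be present. The diabetes term in the steatosis index belongs to a cited formula, and reproducing it does not prove that diabetics are expected. Protocol 7.2 also excludes patients at high risk of developing cardiovascular disease, and the documents do not say whether that captures diabetics. Both remarks stand. Eligibility of controlled diabetics remains the fair reading of an exclusion limited to uncontrolled disease, but their number could be close to zero.

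Three stronger readings are tempting and are not supported:

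- *That every eligible diabetic controlled on medication fails the glucose item.* Control is left to the investigator's judgment with no glucose threshold, so a treated patient at 100 or above meets the item as written.
- *That every treated diabetic below 100 is moved to the without group.* Step 2 shows that losing the item changes the classification only when glucose is the deciding second item.
- *That the subgroup contrast is diluted.* This presumes that LDL response differs by syndrome status, which the documents do not claim. SAP 6.5.4 gives only summary statistics for this classification, and no planned test, interaction term or model uses it. SAP 6.7 says that no subgroup analyses are planned.

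**Conclusion.** The point holds in a narrow form. A diabetic on glucose-lowering treatment whose fasting glucose is below 100 mg/dL is filed as without Metabolic Syndrome when the waist criterion is met and exactly one of the blood-pressure, triglyceride and HDL items is positive. No other section supplies a treatment or diagnosis alternative that would prevent this.

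The size is minor. The number misfiled cannot be derived from the documents and is probably very small; the figure of 1 to 4 rests wholly on assumed prevalences and is a ceiling. The effect is confined to the exploratory descriptive LDL summaries by syndrome status. The primary and secondary ANCOVAs do not use the classification and are unaffected. This is a free improvement in consistency, not a threat to any conclusion of the trial.

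**What to change.** Before unblinding, reword the glucose item in SAP 6.5.4, for analysis classification only, so that it is met by a fasting glucose of 100 mg/dL or more or by current treatment with glucose-lowering drugs for diabetes. This mirrors the blood-pressure item and corrects the unit.

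Derive treatment status at baseline from concomitant medication, which SAP 6.3 says is recorded with its indication, together with the medical history taken at Visit 1. The indication lets the derivation leave out glucose-lowering drugs given for other reasons.

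The cost is one phrase in the SAP and one derivation line. No new data, visit or procedure is needed. Fixing the rule while the data are still blinded keeps it from looking like a choice made after seeing the results.

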2.3. EXPLORATORY OBJECTIVES

Evaluated LDL cholesterol levels and change from baseline focusing on patient subgroups of clinical interest. Evaluated LDL cholesterol decrease between groups of patients

Statistical Analysis Plan

Sponsor: A. Menarini Industrie Farmaceutiche Riunite S.r.l.

Protocol number: MEIF/16/MOF-Col/001

classified according to clinical characteristics at baseline (i.e. LDL levels, eGFR levels, Metabolic syndrome, glucose in fasting conditions altered, proved hypertension).

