3.3. STUDY POPULATION

The study population consists of subjects, aged 30-75 years, with sub-optimal blood LDL-cholesterol levels (LDL-cholesterol = 115 -190 mg/dL and Triglycerides < 400 mg/dL). A total of at least 88 patients meeting the following inclusion and exclusion criteria are to be recruited.

Inclusion criteria

- Age 30-75 years
- LDL-cholesterol = 115-190 mg/dL

Statistical Analysis Plan

Sponsor: A. Menarini Industrie Farmaceutiche Riunite S.r.l.

Protocol number: MEIF/16/MOF-Col/001

- Triglycerides < 400 mg/dL
- Any cardiovascular therapy should be stable for type and dose for at least three months
- Signed, written informed consent

Exclusion criteria

- Intolerance to any ingredient of dietary supplement
- Patients already suffering from cardiovascular diseases or at high risk of developing cardiovascular diseases
- Myopathies
- Uncontrolled diabetes mellitus based on PI judgment
- Chronic renal failure (defined as eGFR<60ml/min/1.73m²) or liver failure (defined as AST and /or ALT>3 Upper Limit of Normal) (ULN)
- Body Mass Index > 32 kg/m²
- Therapy with statins or other drugs or supplements with effects on lipid metabolism
- Patients with acquired immunodeficiency
- Treatment with immunosuppressants
- Pregnant or breastfeeding women
- Women of childbearing potential not willing to use effective birth control methods
- Patients participating in or having participated in another clinical trial within the previous 3 months
- Current or recent history of drug or alcohol addiction based on PI judgment

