3.6. SAMPLE SIZE

Considering the primary endpoint of the study as the reduction from baseline to week 8 in LDL cholesterol level and the data available from literature [Phytomedicine. 2016 Oct 15; 23(11):1113-8], a reduction of LDL level of approximately 10% is expected after the intake of the nutraceutical. Therefore, a mean difference of 15 mg/dL in the reduction of LDL cholesterol level at week 8 between the nutraceutical treatment group and the placebo group is considered clinically significant.

Assuming a baseline LDL level of 145 ± 19 mg/dL, a power of 90% and a 5% two-sided alpha level to detect a difference in mean change in LDL from baseline to week 8 equal to 15 mg/dL between the nutraceutical and the placebo group, the total number of patients to be evaluated should be 35 per treatment arm in a 1:1 ratio (NQuery Advisor, 7.0). Allowing for an approximate 20% dropout rate, at least 88 patients should be randomized: 44 patients in each treatment group.

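### SAP 6.5.4 inverts the altered fasting glucose subgroup: values below 100 mg/dL are classed as altered and values of 100 to 125 mg/dL as not altered

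*SAP*

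**What the plan says.** SAP 2.3 lists, among the baseline characteristics by which the LDL cholesterol decrease is to be compared, "glucose in fasting conditions altered". It gives no cut-off.

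The only operative definition is in SAP 6.5.4: "Patients with/without glucose in fasting conditions altered, defined as glucose in fasting conditions out of the following range: from 100 mg/dl and 125 mg/dl". The subgroup is used in summary statistics of LDL cholesterol level and change from baseline, in the FAS, which "will be presented focusing on patient subgroups of clinical interest".

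A few lines earlier, SAP 6.5.4 gives the components of Metabolic Syndrome. One of them is "Glucose in fasting conditions ≥ 100 mg" (the unit is printed without the per-decilitre part; I read it as mg/dL).

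On who can be enrolled, SAP 3.3 excludes "Uncontrolled diabetes mellitus based on PI judgment". Diabetes as such is not an exclusion.

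**The concern.** The definition puts the middle band, 100 to 125 mg/dL, on the unaltered side and everything else on the altered side. That joins patients below 100 mg/dL with any patients above 125 mg/dL in one group, which fits neither of the two rules the sponsor could plausibly have meant. It also runs against the Metabolic Syndrome component in the same section: a patient at 110 mg/dL would meet that component and yet be tabulated as without altered glucose, and a patient at 85 mg/dL would show the reverse.

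A programmer has nothing else to work from. SAP 2.3 names the group only. The low/normal/high classification in SAP 6.6.2 rests on local laboratory ranges and serves the safety tables. Protocol 11.6 plans no subgroup analyses and so holds no definition to fall back on.

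At stake is the table that answers part of a stated exploratory objective. A statement about LDL response in patients with altered glucose would rest on patients below 100 mg/dL plus any above 125 mg/dL.

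**Working it through.** The plan gives no figure to reproduce here; the check is to apply each rule to the same glucose values.

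**Rules compared** (g = baseline fasting glucose, mg/dL)

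- As written in SAP 6.5.4: altered if g < 100 or g > 125.
- Band reading: altered if 100 ≤ g ≤ 125.
- Threshold reading: altered if g ≥ 100, in line with the Metabolic Syndrome component.

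| g | As written | Band 100–125 | Threshold ≥ 100 |
|---|---|---|---|
| 85 | altered | not | not |
| 99 | altered | not | not |
| 100 | not | altered | altered |
| 110 | not | altered | altered |
| 125 | not | altered | altered |
| 126 | altered | not | altered |
| 140 | altered | not | altered |

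Up to and including 125 mg/dL, the written rule gives the opposite label to both readings. Above 125 mg/dL it agrees with the threshold reading and disagrees with the band reading.

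**Can values above 125 mg/dL occur?** Yes. Only uncontrolled diabetes, as judged by the investigator, is excluded (SAP 3.3). The Hepatic Steatosis Index formula in Protocol 9.3 adds points "if diabetes mellitus", which is compatible with diabetic patients in the trial but does not prove it. Their share is not stated in the documents.

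**How many labels are wrong.** Let p be the share of patients above 125 mg/dL.

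- Band reading: all labels are wrong, 100% for any p.
- Threshold reading: wrong share = 1 − p.

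For N, SAP 3.6 says "the total number of patients to be evaluated should be 35 per treatment arm", so N = 2 × 35 = 70. For p, I assume a range of 0 to 15%.

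| Assumed p | Wrong share, threshold reading | Patients of 70 |
|---|---|---|
| 0% | 100% | 70 |
| 5% | 95% | 66.5 |
| 10% | 90% | 63 |
| 15% | 85% | 59.5 |

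**Wrong label versus wrong row.** Under the band reading, the written rule forms the two intended groups with their names exchanged. Under the threshold reading, exchanging the names is not enough: patients above 125 mg/dL would still be in the wrong row, 0 to 15% of 70, or 0 to 10.5 patients.

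**What the class feeds.** The ANCOVAs in SAP 6.5.1 and 6.5.3 use planned treatment and the baseline value of the variable analysed. The exploratory regressions that involve glucose enter the measured value, "considering patients eGFR and glycemia values at baseline as predictors". Neither depends on this class.

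**The case against.** The strongest reply is that this is a slip of wording in an exploratory section, and that the count of wrong labels overstates the harm. If the band was intended, each row contains the right patients and the right statistics under the wrong name, and a reader who sees the definition can exchange the names. If the threshold was intended, only patients above 125 mg/dL are in the wrong group once the names are exchanged. No test, interval or decision is attached to the table. The Metabolic Syndrome component is one element of another definition, not a rival definition of altered glucose. The assumed share above 125 mg/dL has no source in the documents, and 70 is the planned evaluable number, while at least 88 are to be randomized, so the FAS could be larger.

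Much of this stands. The distinction between a wrong label and a wrong row is correct. The Metabolic Syndrome line shows which direction the same section treats as abnormal and no more than that. The figure of 60 to 70 patients is illustrative.

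It does not remove the defect. A table whose two rows carry each other's names is still a wrong table, and relabelling it needs knowledge of the intended rule, which the SAP does not give. Replacing the outside-range wording with a within-range wording also leaves a gap: patients above 125 mg/dL would then be counted as without altered glucose, and the SAP does not say whether that is meant.

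**Conclusion.** The definition is wrong as written and should be corrected. For every value at or below 125 mg/dL the label is the opposite of what either plausible rule would give; this follows from the text and needs no assumption. The share of mislabelled patients is 100% under the band reading. Under the threshold reading it is 100% less the share above 125 mg/dL: 85 to 100%, or about 60 to 70 of 70, if that share is 0 to 15%. Both that range and the use of the planned 70 as denominator are assumptions.

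The consequence is confined to one descriptive exploratory summary. It affects neither the primary result, nor the secondary analyses, nor the regressions on glucose.

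**What to change.** Before database lock and unblinding, amend the sentence in SAP 6.5.4 so that patients below 100 mg/dL are outside the altered group and patients at 100 to 125 mg/dL are inside it. The sponsor should say which of these was meant:

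- (a) baseline (Visit 2) fasting glucose of 100 mg/dL or more, which matches the Metabolic Syndrome component; or
- (b) baseline fasting glucose from 100 to 125 mg/dL inclusive, with values above 125 mg/dL reported in a separate, stated class.

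If the intention cannot be established, three rows (below 100, 100 to 125, above 125 mg/dL) serve both readings.

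The cost is one line of SAP text and the matching derivation of the subgroup flag. No new data are needed, because glucose is already measured at Visit 2. Protocol 11.8 requires the SAP to be final before database lock, and settling the rule by then avoids choosing a subgroup definition with the treatment codes known.
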